8.1 NORMAL OR ADAPTIVE SYMPTOMS

Transient symptoms such as end-of-day dryness, lens awareness, itching or burning or other discomfort may occur with contact lens wear and may occasionally reduce wearing time. These are not reported as adverse events unless in the investigator's opinion they are unexpected in nature, severe or have a high rate of occurrence.

8.2 PROCEDURES FOR ADVERSE EVENTS

Treatment of an adverse event will depend on its nature and severity. Based on the clinical judgment of the investigator the participant may be managed at the practice or referred to another eye care practitioner for treatment. The investigator will attempt to determine whether the reaction is related to the test device or a result of other factors. An adverse event form will be completed for each adverse event. If both eyes are involved, a separate adverse event form will be completed *for each eye*. Whenever possible, the adverse event will be photo-documented.

[figure not shown]
Expenses incurred for medical treatment as part of study participation will be paid by the sponsor (bills and prescription receipts kept). The participant must be followed until resolution or no further change is anticipated and/or referred for further care with the appropriate health care professional and/or recorded as being under appropriate health care as per investigator's discretion. A written report will be completed indicating the subsequent treatment and resolution of the condition.

8.3 REPORTING ADVERSE EVENTS

All potential Serious and Unanticipated Adverse Device Effects that are related or possibly related to participant's participation will be reported to CORE's lead study coordinator (details below) and also to the sponsor (details below) within 24 hours of the investigator becoming aware of the event.

The site's Principal Investigator will also report the event to Sterling IRB within 10 business days of becoming aware of the Serious or Unanticipated event, using the Reportable Events Form. All fatal or life-threatening events will be reported immediately to the IRB.

Significant and Non-Significant Adverse Events will be reported to CORE's lead study coordinator and the sponsor as soon as possible, but no later than 5 working days after becoming aware of it.

Details of all adverse events will be included in the study report.

9 DISCONTINUATION FROM THE STUDY

Participants may be discontinued at the discretion of the investigator or sponsor in consideration of participant safety or protocol compliance, or at discretion of the participant. Participants discontinued from a study will be reimbursed per visit for their active involvement in the study (including the initial screening visit and all lens fitting visits). Upon discontinuing, a participant will be offered the option of their data being withdrawn from future statistical analysis. The following is a list of possible reasons for discontinuation from the study:

 Screening failure: Participants will be discontinued if they do not meet the inclusion and exclusion criteria outlined in section 5.2.3.

- Unacceptable performance with products to be used in study: Participants may be discontinued if they are unable to achieve acceptable comfort and /or vision with the study products.
- Positive slit lamp finding: Participants may be permanently discontinued from the study depending on the severity of the condition and on the judgement of the investigator.
- Adverse event: If a participant experiences an adverse event during the study they may be discontinued based on the clinical judgement of the investigator.
- Symptoms: If the participant has persistent symptoms, they may be discontinued based on the clinical judgement of the investigator.
- Disinterest, relocation or illness: The participant may choose to discontinue due to reasons within or beyond their control.
- Violation of protocol or non-compliance: The participant will be discontinued if they are unable or unwilling to follow the protocol specified visit schedules and/or study procedures.
- Instillation of topical ocular medication: The participant will be discontinued if they elect to use a topical ocular medication during the study unless that topical ocular medication is prescribed for a limited duration (less than two weeks) to treat a transient condition; in this case the participant may remain an active participant (at the discretion of the investigator) after stopping topical ocular medication following resolution of the ocular condition).
- Lost to follow-up: The participant will be discontinued if they cannot be contacted and do
 not return to complete the final study exit, and if the investigator has made a reasonable
 effort to contact the participant for a final study visit.
- Premature termination of the study by the sponsor, CORE or Sterling IRB.

A discontinuation form, stating the reason for discontinuation will be completed, which requires the signatures of both the participant and the investigator except where the participant is lost to follow-up in which case only the signature of the investigator is required.

When a participant chooses to discontinue from the study, they will be given the opportunity to withdraw their data from the statistical analysis. This choice will be captured on the discontinuation form.

All discontinuations including their reasons will be included in the final report.

10 DEVICE MALFUNCTIONS

A device malfunction means the failure of the device to meet its performance specification or otherwise perform as intended. Any defective lens that is *likely* to cause or contribute to a *Serious Adverse Event* should be reported to CORE and the sponsor **within 24 hours** of the investigator becoming aware of the malfunction. STERLING IRB would also be notified within 10 business days of any device malfunction that may contribute to a *Serious Adverse Event*.

Other defective lenses should be reported to CORE as soon as possible.

This clinical study will also ascertain satisfaction or preference with subjective attributes such as comfort, vision, or lens handling. Responses to these subjective questionnaires will not be considered as complaints or device malfunctions.

11 STUDY COMPLETION AND REMUNERATION

At the last scheduled protocol visit a study completion form will be completed, which requires the signatures of both the participant and the investigator. Participants will also be provided with a letter of appreciation.

Once their involvement in the study is complete, participants will be informed about receiving feedback following study completion in the Letter of Appreciation.

[figure not shown]
Participant remuneration will be provided at the end of their study involvement.

12 STATISTICAL ANALYSIS AND DATA MANAGEMENT

12.1 STATISTICAL ANALYSIS

All data will be analyzed by CORE at the University of Waterloo. Unmasked data analysis will be conducted using Statistica 10, Statsoft or other suitable software. Descriptive statistics will be provided on demographic data (age, gender, refractive error distribution, etc.). Table 6 lists the primary and other outcome variables and anticipated statistical procedures.

Comparisons will be made between the study lenses for the variables measured at the 1-month visits. Additionally, the subjective ratings completed on days 1, 7, 14, 21 and 27 with each study lens will be compared.

Additional analysis may be conducted.

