3 OBJECTIVES

To evaluate the clinical performance of two monthly silicone hydrogel contact lenses in habitual wearers of frequent replacement (FRP) lenses when worn for 1-month.

The primary outcome variable for this study is:

 Lens handling on removal (0-10 scale, 0.5 steps) collected in the Day 27 At-Home Subjective ratings.

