4 HYPOTHESIS

The null hypothesis is that there will be no difference for lens handling on removal on day 27 between Lens A compared to Lens B, captured in the Day 27 At-home Subjective Ratings form.

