5 MATERIALS AND METHODS

5.1 STUDY DESIGN

5.1.1 OVERALL DESIGN

This study is a prospective, bilateral eye, double-masked, randomized, 1-month cross-over, daily-wear design involving two different FRP lens types. Each lens type will be worn for approximately one month, during which participants record their subjective lens-wear experience on several different days at home and during study visits.

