5.1.3 MASKING

At the fitting visit, only the participant will be masked of the lens type, the investigator will know which type is being fit in order to make changes to the lens at this visit if needed.

At both dispense visits, participants and investigators will be masked to the lens type dispensed. In order to achieve this, unmasked study personnel will determine the lens order according to the randomization schedule and will over-labeled the lens packages/foils prior to dispense.

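### Section 12.1 prescribes unmasked analysis, and nothing requires database lock or a settled analysis population before the analysts know which lens is which

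*Combined protocol and SAP*

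**What the plan says.** Section 12.1 gives the rule for the analysts: "Unmasked data analysis will be conducted using Statistica 10, Statsoft or other suitable software". It then says "Table 6 lists the primary and other outcome variables and anticipated statistical procedures" and closes with "Additional analysis may be conducted". Table 6 is not in the supplied text.

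Section 5.1.1 describes the design: "This study is a prospective, bilateral eye, double-masked, randomized, 1-month cross-over, daily-wear design involving two different FRP lens types". Section 5.1.3 says whom the masking covers. For dispensing: "At both dispense visits, participants and investigators will be masked to the lens type dispensed". For fitting: "At the fitting visit, only the participant will be masked of the lens type". Analysts are not mentioned in either place.

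Two sections fix the primary comparison in advance. Section 3 names the outcome: "Lens handling on removal (0-10 scale, 0.5 steps) collected in the Day 27 At-Home Subjective ratings". Section 4 states what will be tested: "The null hypothesis is that there will be no difference for lens handling on removal on day 27 between Lens A compared to Lens B".

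Section 5.5 treats visits outside their windows as protocol deviations. Whether those data enter the analysis population is to be judged when the study ends. It gives no criteria and does not say whether the judgement is made masked.

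**The concern.** The trial compares a CooperVision lens (Lens A) with a competitor's on one subjective 0-10 rating. CooperVision reimburses study product (Section 5.4) and registers the trial (Section 15.3); I take it to be the sponsor, although the supplied text does not say so outright. Sites over-label the foils so that neither participant nor investigator knows the lens dispensed. That protection stops at the analysis, where lens identity is open by rule and no reason is given for needing it.

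Knowing the lens at analysis cannot change a rating already written on a form. It can influence, even unintentionally, a decision still to be made: whether a participant with an out-of-window visit stays in, which test is reported if more than one is defensible, and which extra analyses are shown. If those decisions come after lens identity is known, a result favouring either lens is easier to challenge, and the sponsor cannot show from the plan that the decisions were neutral.

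**Working it through.** **1. The plan's own figure.** Section 5.3.1 gives a two-tailed t-test, alpha 0.05, paired difference 1.0, and power 0.805637, 0.842360 and 0.901677 at n = 60, 66 and 79. The SD of the paired difference (σ) is not stated, so I solved it from the first row.

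- Formula: power = P(|T| > t₀.₉₇₅,ₙ₋₁), where T is noncentral t with n − 1 df and noncentrality 1.0 × √n / σ.
- At n = 60, σ = 2.70 gives noncentrality 7.746 / 2.70 = 2.87 and power 0.805637.
- The same σ gives 0.842360 at 66 and 0.901677 at 79. All three rows match to six decimals.
- A two-sample t-test solved the same way gives 0.841806 and 0.900523 at 66 and 79, which is close but not exact.

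Sizing therefore used a paired t-test. That indicates the intended primary test, but it is not a statement of the analysis test. That statement would be expected in Table 6.

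**2. What is fixed, and when.**

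| Item | Where | Status |
|---|---|---|
| Primary outcome, scale, form, day | Section 3 | Fixed in advance |
| Null hypothesis, Lens A versus Lens B | Section 4 | Fixed in advance |
| Test used for sizing | Section 5.3.1 | Paired, two-tailed, alpha 0.05 |
| Test for the primary analysis | Table 6 | Not available; Section 12.1 calls the procedures anticipated |
| Data from out-of-window visits | Section 5.5 | Judged at study end, no criteria |
| Additional analyses | Section 12.1 | Allowed, no label |
| Database close | Section 15.7 | Mentioned only for record retention |
| Time at which analysts are unmasked | – | Not stated |

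The last five rows are the point. No sentence puts any of them in order relative to the release of lens identity.

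**3. Why the population decision matters.** The comparison is paired, so excluding one period for a participant removes that participant's pair. The Day 27 form is completed at home before the follow-up visit, so it is not certain that a late visit would affect it. Section 5.5 speaks of the analysis population, however, so the primary dataset is within reach of the judgement.

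**4. Who holds the key.** Section 5.1.2 has the CORE Database Administrator generate the schedule and give it to research assistants at each site. Under Section 15.7 the dispensing logs go to CORE when the study is complete. Section 12.1 has CORE analyse all the data. No separation of key-holder and analyst is described.

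**5. Can the benefit of coding be given as an error rate?** I tried and rejected this. In 20,000 simulated null trials (60 pairs, σ = 2.70, differences in 0.5 steps), the t-test alone rejects 5.1% of the time. The better of t-test and Wilcoxon rejects 6.0%, and the best of those and the sign test 7.3%. If 3 or 6 of the 60 (assumed numbers) could be kept or dropped after seeing results, the t-test alone rejects 6.2% or 6.7%.

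Swapping the lens labels turns every difference d into −d and leaves each two-sided p-value unchanged. An analyst working on codes X and Y could make the same selections and reach the same rates. By symmetry, half of each rate falls on either lens: 5.1 / 2 = 2.55%, 6.0 / 2 = 3.0%, 7.3 / 2 = 3.65%. Coding takes away the ability to aim the selection at one lens. Only fixing the test and the population in advance removes the inflation.

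**The case against.** The strongest reply is that unmasked analysis is an openly declared choice and breaks nothing. Much of that stands.

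- A reader might infer that Section 12.1 conflicts with the double-masked label. It does not: Section 5.1.3 masks participants and investigators, and the rating is the participant's own.
- A reader might infer that the blind ends before the lens comparison is fixed. The documents do not support this. They give no time of unmasking, and the wording is compatible with unmasking after database close. Sections 3 and 4 fix the outcome, day and hypothesis, and sizing used a paired two-tailed t-test.
- A reader might infer that the statistical procedures were left open. Table 6 may name a single primary test; its absence from the supplied text is not a fault in the plan. The word anticipated is the only visible evidence of openness.
- The free choice of software has little bearing on bias. The five at-home rating days matter little here, because only Day 27 is primary.
- Coding requires a separation of roles within CORE that the documents do not describe, so it is not entirely free.

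What the reply does not meet is the missing order of events. Section 5.5 leaves a real decision to the end of the study without criteria, Section 12.1 makes the analysis unmasked, and nothing places the first before the second.

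**Conclusion.** The point holds as a cheap improvement, not as a contradiction or an invalid analysis. The plan prescribes unmasked analysis, leaves the out-of-window decision to an end-of-study judgement without criteria, and does not label additional analyses. It does not say that lock and these decisions come before lens identity is known. The exposure is to choices made in one lens's favour about the analysis population and any test that Table 6 does not fix.

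Its size cannot be stated from the documents. It depends on how many participants have out-of-window visits, what Table 6 specifies and when the analysts are unmasked, none of which is known. The simulated rates above should not be read as the gain from coding. No misconduct is assumed, and the sample size of 60 is unaffected. If Table 6 names one primary test, the remaining exposure for the primary outcome is the analysis population.

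**What to change.** Replace the unmasked-analysis sentence in Section 12.1 with wording such as:

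> The Section 5.5 decisions on protocol-deviation data and the primary test will be made final, and the database locked, before lens identity is released to the analyst. The Table 6 comparisons will be run on lens codes X and Y, with the key held by the Database Administrator until they are final. Analyses added after release will be labelled post hoc.

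Add a cross-reference in Section 5.5 so that the two sections agree on when the population decision is made.

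The cost is one recoded column in the export, with lens names merged into the tables at the end. In addition, CORE must keep the analyst away from the randomization schedule (Section 5.1.2) and the dispensing logs it receives (Section 15.7) until release, and should name who does this. Sample size and visits are unchanged.

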12.2 DATA MANAGEMENT

Data will be collected and written on paper forms which will be provided to each site by CORE. Each site will be instructed to send completed study forms to CORE using a secure file share system operated by the University of Waterloo called Sendit which uses 128bit (or 256bit) SSL encryption. The sites will receive their individual accounts and passwords.

The site will endeavour to send the scanned forms to CORE on the same day as the study visit or a maximum of two days after the study visit.

Within CORE, data will be entered into a REDCap database developed and tested specifically for this study and accessible only to trained, authorised users. A data management plan will be developed to describe the data handling in more detail, including the personnel involved.

Data from this study will be retained by CORE for a minimum of 25 years on a passwordprotected server. After 25 years, data will be disposed of in accordance with the guidelines laid out by the University of Waterloo. More details regarding storage procedures are provided in section 15.7 and also in CORE SOP014 Clinical data management.

At the completion of the study CORE will provide a copy of the study database in Excel format to the sponsor when requested. Data will typically be sent using Sendit. This system provides a secure way to transfer files when email is not appropriate, whether because of file size, file type or concerns over security. Sendit includes features such as password protection, a restricted time period for download, IP logging and email notification of download. Files may be encrypted prior to transmission at the request of the sponsor. Using this method means that data files are only stored on University of Waterloo servers during the transfer.

12.3 COMMENTS ON SOURCE DOCUMENTS

Data analysis will not be conducted on comments which have been recorded in the source documents. Only relevant and applicable comments will be included in the final report as deemed necessary by CORE's Lead Coordinator.

13 PROTOCOL & OTHER TRAINING

All study personnel will be required to complete training prior to their involvement in the study. Records of training will be kept at CORE. This will include training by CORE on the study protocol, study procedures, informed consent procedures, and on the randomization and participant masking procedures, as well as training for Good Clinical Practice.

All site Principal Investigators and co-investigators will provide CooperVision Inc with a scan of their curriculum vitae, license to practice optometry and evidence of professional indemnity insurance.

14 STUDY MONITORING

Each site will provide regular status reports to CORE. Status reports will include:

- These may include but are not limited to participant enrollment status, cases of discontinuation etc.
- Details of all protocol deviations, adverse events, device malfunctions.
- Reports of unintended events.

CORE will collate the site updates and provide frequent status reports to the study sponsor.

Study monitoring visits to the sites may be conducted by CORE, the sponsor, or sponsor's designate, throughout the study and will be scheduled in conjunction with the Principal

EX-MKTG-129 STARFISH Protocol v1.2 30sep2021

Investigator at each site. In addition, study records may be inspected by the sponsor, the sponsor's designate, Sterling Institutional Review Board, and by regulatory authorities in Canada and the United States, namely Health Canada and the United States Food and Drug Administration (FDA); however, they will not be permitted to take away any records containing identifiable personal information.

Study data review and data monitoring will be conducted by CORE personnel. To improve data integrity, data entry will be conducted by two people and the entries will be compared. Data queries will be reported to the site within 5 working days of receipt of initial data. A response resolving the query will be expected from the site within 5 working days of receipt of the query.

All adverse events and protocol deviations will be reviewed by the site Principal Investigator and CORE's Lead Coordinator. All serious adverse events and major protocol deviations will be reviewed by the site Principal Investigator and CORE's Director and/or Head of Clinical Research.

15 STUDY MANAGEMENT

15.1 STATEMENT OF COMPLIANCE

This clinical study is designed to be in compliance with the ethical principles in the Declaration of Helsinki, with the ICH guidelines for Good Clinical Practice (GCP), with the University of Waterloo's Guidelines for Research with Human Participants and with the Tri-Council Policy Statement: Ethical Conduct for Research Involving Humans, 2nd Edition.

- Declaration of Helsinki
- ICH E6 International Conference on Harmonisation; Good Clinical Practice
- http://iris.uwaterloo.ca/ethics/human/guidelines/index.htm
- http://iris.uwaterloo.ca/ethics/human/ethicsReview/UWStatement.htm
- http://www.pre.ethics.gc.ca/eng/policy-politique/initiatives/tcps2-eptc2/Default/

Informed consent shall be obtained in writing from the participant and the process shall be documented before any procedure specific to the clinical investigation is carried out.

15.2 ETHICS REVIEW

This protocol will be submitted to and reviewed through the Sterling Institutional Review Board. Notification of ethics clearance of the application is required prior to the commencement of the study. This study will be conducted in accordance with Institutional Review Board regulations (U.S. 21CFR Part 56.103) or applicable IEC regulations. Copies of all IRB/IEC correspondence with the investigator/sponsor will be kept on file. The study will commence upon approval from the following Institutional Review Board: Sterling Institutional Review Board; Telephone number: [contact] and email address: [contact].

